## LIST OF ABBREVIATIONS

ACCORD	Academic and Clinical Central Office for Research & Development - Joint office for University of Edinburgh and NHS Lothian
AE	Adverse Event
AF	Atrial Fibrillation
AMU	Acute Medical Unit (or equivalent)
AR	Adverse Reaction
CHSS	Chest, Heart & Stroke, Scotland
CRF	Case Report Form
CV	Curriculum Vitae
GCP	Good Clinical Practice
ECG	Electrocardiogram
ED	Emergency Department
EMERGE	Emergency Medicine Research Group of Edinburgh
EPR	Electronic Patient Record
ICH	International Conference on Harmonisation
IMP	Investigational Medicinal Product
ISF	Investigator Site File
MACE	Major Adverse Cardiac Event
NYHA	New York Heart Association
QA	Quality Assurance
R&D	Research and Development
REC	Research Ethics Committee
SAE	Serious Adverse Event
SAR	Serious Adverse Reaction
SOP	Standard Operating Procedure
SUSAR	Suspected Unexpected Serious Adverse Reaction
SVT	Supraventricular Tachycardia
TMF	Trial Master File
UAR	Unexpected Adverse Reaction
VF	Ventricular Fibrillation
VT	Ventricular Tachycardia

## **SUMMARY**

Palpitations (noticeable pounding, fluttering or irregular heart beat) and pre-syncope (near blackout) are common ED problems sometimes due to an abnormal cardiac rhythm. This is difficult to diagnose as examination and electrocardiogram (ECG) are commonly normal and symptoms have usually resolved by the time the patient arrives in the ED. Diagnosing an abnormal heart rhythm as the cause of symptoms rests on capturing it on an ECG and patients are usually discharged with advice to return to the ED again for a 12-lead ECG should symptoms recur. We believe a smart phone based event recorder will allow better and earlier diagnosis in patients with a compatible smart phone or tablet, and revolutionise ED care in this area.

# 1 INTRODUCTION

## 1.1 BACKGROUND

Palpitations (the noticeable pounding, fluttering or irregular beating of the heart) and pre-syncope (the sudden onset of a sense of impending loss of consciousness) are together responsible for 1.0% of ED visits (300,000 annual ED attendances in the UK) [1,2]. They are less likely to be due to serious arrhythmia than syncope (sudden onset of brief loss of consciousness) and are more likely due to conditions such as atrial fibrillation (AF) and supraventricular tachycardia (SVT). Diagnosis of the underlying rhythm is difficult as many patients are fully recovered on ED arrival and examination and presenting ECG are commonly normal. Many episodes are due to benign causes such as anxiety or frequent ectopics (extra or skipped heart beats).

The only way to establish the underlying heart rhythm is to capture an ECG during symptoms. Many patients go for years without diagnosis due to the difficulty in capturing the underlying heart rhythm. 12-lead ECG and conventional ambulatory devices are of limited use due to the infrequency of symptoms in many patients. Most are discharged from the ED and asked to represent or phone 999 should they get further symptoms in the hope of capturing the episode on a standard 12-lead ECG.

Recent technology advances have led to several novel ECG monitoring devices appearing on the market. The Emergency Medicine Research Group, Edinburgh (EMERGE) with CHSS support, is currently evaluating a continuous ambulatory ECG monitor (ZIO@XT Patch) for use in syncope patients. This is a pilot study aiming to recruit 100 participants by December 2016. Devices that continuously monitor are vital to detect underlying cardiac rhythm in patients with syncope as the patient has lost consciousness and is therefore not able to use devices that require the patient to trigger the ECG recording (event recorders).

The pocket sized AliveCor Heart Monitor and AliveECG phone/tablet app is a monitoring device that requires the patient to trigger the ECG recording. It is available for both Apple and Android mobile and tablet operating systems and was CE marked in January 2015 [3]. With minimal training, two fingers from each hand are placed on the monitor (which can be connected to the back of a smart phone) for 30 seconds to take an ECG recording, which is transmitted wirelessly to the app, analysed and synchronised to an encrypted server. The patient can then alert their healthcare professional to allow their ECG to be viewed securely [3].

The Arrhythmia Alliance [3] distributed AliveCor Heart Monitors to 1500 people of all ages. Only one returned their monitor because it caused them to worry and check their heart rate too often. 26% of recordings showed a previously undetected arrhythmia and 5% were advised to see their doctor urgently. They reported the AliveCor Monitor was 'easy for people of all ages to use, and could save money for the NHS when compared with the cost of standard NHS ECG recordings.' Older people were also noted to be regular users of mobile technology and gave positive feedback about the system.

## 1.2 RATIONALE FOR STUDY

There have been few studies investigating the use of smart phone based event recorders [4-7], and none in an acute or ED population, where large numbers of patients present. We believe this smart phone event recorder will allow ED patients who have presented with palpitations or pre-syncope to record their ECG tracing if they have a further episode increasing the rate of underlying rhythm diagnosis.

## **2 STUDY OBJECTIVES**

### **2.1 OBJECTIVES**

#### **2.1.1 Primary Objective**

To compare the symptomatic rhythm detection rate at 90 days of a smart phone based event recorder (AliveCor Monitor) compared to standard care for participants presenting to the ED with palpitations and pre-syncope with no obvious cause in the ED.

#### **2.1.2 Secondary Objectives**

1. To investigate the symptomatic rhythm detection rate for cardiac arrhythmia detection at 90 days of a smart phone based event recorder compared to standard care for participants presenting to the ED with palpitations and pre-syncope
2. To compare the time to detection of symptomatic rhythm versus standard care
3. To compare the time to detection of cardiac arrhythmia versus standard care
4. To compare the number of participants treated or (planned for treatment) for cardiac arrhythmia versus standard care
5. To investigate participant satisfaction and monitor compliance
6. To compare the cost of symptomatic rhythm detection at 90 days of a smart phone based event recorder compared to standard care for participants presenting to the ED with palpitations and pre-syncope
7. To compare serious outcomes at 90 days in participants using a smart phone based event recorder compared to standard care

#### **2.1.3 Primary Endpoint**

Symptomatic rhythm detection rate of a smart phone based event recorder for symptomatic rhythm detection at 90 days versus standard care.

#### **2.1.4 Secondary Endpoints**

1. Symptomatic rhythm detection rate of a smart phone based event recorder for cardiac arrhythmia detection at 90 days versus standard care
2. Time to detection of symptomatic rhythm using a smart phone based event recorder versus standard care
3. Time to detection of cardiac arrhythmia rhythm using a smart phone based event recorder versus standard care
4. Number of participants treated or (planned for treatment) for cardiac arrhythmia in participants using a smart phone based event recorder versus standard care
5. Participant satisfaction and monitor compliance
6. Cost effectiveness analysis
7. Serious outcomes at 90 days: all cause death and major adverse cardiac events [MACE] (myocardial infarction, life-threatening arrhythmia, insertion of a pacemaker or internal cardiac defibrillator, insertion of pacing wire).

## **3 STUDY DESIGN**

This is a multi-centre hospital ED / AMU open label, randomised controlled trial of participants aged 16 years or over presenting with an episode of palpitations or pre-syncope and whose underlying ECG rhythm during these episodes remains undiagnosed after ED assessment. Participants will be followed-up at 90 days using hospital records, contacting participant GP and also by contacting the participants themselves. This study is expected to take around 18 months to complete from first participant recruited to last participants' 90-day follow-up.

## **4 STUDY POPULATION**

### **4.1 NUMBER OF PARTICIPANTS**

242 consecutive participants aged 16 years or over presenting with an episode of palpitations or pre-syncope and whose underlying ECG rhythm during these episodes remains undiagnosed after ED assessment shall be recruited into the study. Recruitment will last around 15 months.

### **4.2 INCLUSION CRITERIA**

1. Participant aged 16 years or over
2. Participant presenting with an episode of palpitations or pre-syncope with no obvious cause
3. Participant's underlying ECG rhythm during these episodes remains undiagnosed after clinical assessment.

### **4.3 EXCLUSION CRITERIA**

1. Prior diagnostic ECG
2. Palpitations or pre-syncope present during an admission ECG
3. Frequent episodes (i.e. at least once a day)
4. Participants under 16 years of age
5. Previous participation in the study
6. Alcohol / illicit drugs / seizure / stroke / transient ischemic attack / head trauma / hypoglycemia as presumptive cause
7. Inability or unwilling to give informed consent.
8. Participants with recent (i.e. within 3 months) myocardial infarction, severe heart failure (NYHA class 4) or unstable angina
9. Participants unwilling or unable to use the AliveCor Heart Monitor and AliveECG app
10. Participants without a compatible smart phone or tablet
11. Participants with cardiac pacemakers or other implanted electronic devices
12. No telephone number for follow-up
13. Participant in custody

### **4.4 CO-ENROLMENT**

Co-enrolment will be permitted with non-interventional studies that involve data collection only. Co-enrolment with another interventional study may be allowed provided this is not expected to place an undue burden upon participants and their families, and will not compromise the primary end-point of either study. Consideration will also be given to the burden on the participant. Co-enrolment will only be permitted with agreement of the Chief Investigators of both studies.

## **5 PARTICIPANT SELECTION AND ENROLMENT**

### **5.1 IDENTIFYING PARTICIPANTS**

The research nurses, where it is locally agreed that they are part of the clinical care team, will identify patients using triage information and clinical or electronic records in the ED or the AMU. In this case, it is anticipated they would identify patients and make the first approach. Any member of the clinical team who has received general and trial specific training and is on the delegation log may also identify patients in this way.

If research nurses are not considered to be part of the direct care team locally, activities carried out prior to consent (including identification) will be carried out by a member of the direct care team.

Where research nurses are not considered to be part of the care team, the research nurse should ask a member of the direct care team to identify suitable patients and ask permission from the patient to be approached by the research nurse to discuss participation.

## **5.2 CONSENTING PARTICIPANTS**

If the potentially eligible participant fulfils the study eligibility criteria, a member of the study research team (or direct care clinician if suitably trained) will take written consent.

The participant is assessed by the direct care team to establish if he/she is competent and has capacity to consent. This assessment will be documented in the medical notes i.e. this participant is eligible and capable of providing written informed consent. Participants lacking capacity who are unable to provide consent will not be approached to take part in the study.

The participant (and, if present and appropriate, their accompanying relative) will be given a Participant Information Sheet, which will explain the aims of the study and the potential risks and benefits of the study procedures/tests.

The participant will be given enough time to consider the study and ask questions regarding their participation in the study. For some participants this could be as much as an hour but for others may only be 10-15 minutes. If the participant agrees, informed consent will be confirmed with a signature on the study consent form. The original consent form will be filed in the Investigator Site File (ISF), the participant will receive a copy of this document and a copy will be filed in the participant's medical notes.

Potential, eligible participants who are able to express their consent and able to complete the consent form will be asked to provide written consent. The recruiting direct care clinician or member of the research team will do this. A witness will sign to confirm that all the study information was given and the participant consented to taking part in the study for participants who are able to express their consent but unable to sign.

## **5.3 SCREENING FOR ELIGIBILITY**

There is a requirement to ensure Good Clinical Practice for published studies and to include a Consort diagram [8] of numbers of participants with the study condition during the study period who for one reason or another were not enrolled in the study. In order to determine the number of eligible but not recruited participants during the study period, the ED patient record of all potentially eligible participants will be interrogated by a member of the study research team (if part of the participant's direct care team).

An anonymised log will be kept for patients who were screened for the study and those who were subsequently found to be ineligible or who were not recruited.

## **5.4 INELIGIBLE AND NON-RECRUITED PARTICIPANTS**

Non-recruited but potentially eligible participants will be identified by a daily search of all acute patient admissions records to assess for potential selection/recruitment bias. Ineligible patients will not be recorded.

## **5.5 RANDOMISATION**

### **5.5.1 Randomisation Procedures**

Participants will be equally distributed between the two study arms with 121 participants in each arm. Randomisation will be by block randomisation. Randomisation codes will be generated and blinded envelopes will be prepared and labelled in accordance with the randomisation list for each participating site. Randomisation codes will be held by each recruiting ED in an area of the ED accessible to the research team. Participants eligible for inclusion should be randomised by taking the next lowest consecutively numbered envelope.

### **5.5.2 Treatment Allocation**

Participants will be allocated either to (a) STUDY arm; standard care plus the use of a smart phone based event recorder or (b) CONTROL arm; standard care, depending on the group allocated in the study envelope.

### **5.5.3 Withdrawal of Study Participants**

If a participant wishes to withdraw from the study they will be removed. We will establish whether they consent to allow the use of all data collected up to the date of removal. They will not be replaced.

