### **6.2 STUDY ASSESSMENTS**

Potentially eligible ED and AMU participants will be identified and assessed for study inclusion by the attending clinician. Written consent will be taken and participants will have a Case Report Form (CRF) completed and a 12-lead ECG taken if not already performed by the clinical team.

All STUDY arm participants will be given an AliveCor Heart Monitor and trained in the use of the device and app in the ED or AMU by the research team.

CONTROL arm participants will receive no other intervention.

Participants in both groups will be admitted, referred or discharged by the treating clinician according to current local hospital protocols.

Participants in both groups will be followed up at 90 days through hospital record systems (paper or electronic depending on local policy), GP records and by telephone by the local study team. Participants will also be asked to complete a standardised written questionnaire and will receive a follow-up telephone call from the local study team enquiring about symptoms and contact with medical services. Participants will also be asked about satisfaction and compliance with the heart monitor.

Participants allocated to the Study arm may be contacted by telephone by the local research team shortly after randomisation in the event of them requiring further training or setting up of the device. For example, this may be necessary if a participant does not have their app store password with them in the ED or AMU. If a local electronic patient record system is available, then a research alert will be placed on this stating that the participant has consented to be part of the IPED study.

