### **8.2 PROPOSED ANALYSES**

Descriptive analysis of participant characteristics shall be presented split by study arm. Baseline to 90 day change in diagnostic yield between the two study arms will be analysed using two sample t-tests or non-parametric equivalent as appropriate. Log-rank tests and Kaplan-Meier curves shall be used to examine if the smartphone recorder has an effect on detecting symptomatic rhythm and cardiac arrhythmia separately up to 90 days versus standard care. Categorical variables will be compared using a  $\chi^2$  test (and  $\chi^2$  test for trend if appropriate). All participants will be analysed on an intention to treat basis.

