## ***5. General Considerations***

### **5.1. Overall**

For all analyses, unless otherwise specified, participants shall be analysed according to treatment received, irrespective of the treatment group they were allocated to, with the exception of AE/SAEs. An additional table will be provided on whether the participant took part in the study and if they did not then their AE/SAEs will be included as part of the control group.

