#### **5.1.2. Missing data**

No imputation for missing data shall be performed. The primary outcome analysis will only be performed on those participants with 90 day follow up, however a table to data completeness shall be provided which will capture any participants who were lost to follow-up.

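### Protocol 5.5.3 removes anyone who withdraws without asking whether the day-90 record check may continue, so some primary and serious-outcome data are lost avoidably

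*Protocol*

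**What the plan says.** Protocol 5.5.3 is the whole withdrawal rule, in three steps:

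- The consequence of asking to leave is stated first: "If a participant wishes to withdraw from the study they will be removed".
- Only one question is then put, and it looks backwards: "We will establish whether they consent to allow the use of all data collected up to the date of removal".
- On the number recruited, the rule is brief: "They will not be replaced".

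Protocol 6.2 sets out the 90-day outcome sources: "Participants in both groups will be followed up at 90 days through hospital record systems (paper or electronic depending on local policy), GP records", together with a telephone call. SAP 4.2.2 repeats this.

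On analysis, protocol 8.2 states: "All participants will be analysed on an intention to treat basis". SAP 5.1.2 states: "The primary outcome analysis will only be performed on those participants with 90 day follow up", and adds: "No imputation for missing data shall be performed". A data completeness table will show who was lost. The general rule in SAP 5.1, which applies unless otherwise specified and not to adverse events, is that "participants shall be analysed according to treatment received, irrespective of the treatment group they were allocated to".

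Protocol 9 and SAP 2.3 collect death and major adverse cardiac events as a 90-day endpoint and not as adverse events.

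**The concern.** The record check at day 90 needs no contact with the participant and is already planned for everyone. Section 5.5.3 gives it up for anyone who withdraws, because it asks only about data gathered before removal and the check comes afterwards. SAP 5.1.2 then drops the participant from the primary comparison. On a plain reading this includes someone whose rhythm was captured before leaving and who allowed those data to be used.

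Three things are at stake.

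- **Primary outcome.** The trial is open label, so reasons for leaving can differ between arms. A complete-case comparison is then open to bias, and neither document plans a sensitivity analysis for missing primary outcomes.
- **Serious outcomes.** Death and major cardiac events are captured through the 90-day follow-up and not through adverse event reporting. For a removed participant, no other route is stated for events after removal.
- **Consistency between sites.** Section 5.5.3 does not separate leaving the study from stopping the recorder, the diary or the calls. One site could keep such a participant in follow-up while another removes them.

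**Working it through.** **1. Does the loss follow from the text?** No sentence says that record follow-up stops. It follows from two parts of protocol 5.5.3 read together: the participant is removed, and permission is sought only for data up to removal. The day-90 check falls after that date. SAP 5.1.2 then excludes anyone without 90-day follow-up and imputes nothing.

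**2. The plan's own figures (protocol 8.1).** Inputs are 25% versus 10% detected, 80% power and 110 per arm. The significance level is not stated; two-sided 5% is assumed. A pooled two-proportion calculation gives 100 per arm, or 113 with continuity correction. Exact Fisher power at 110 per arm is 80.4%, so 110 is reproduced. With the allowance, 110 × 1.10 = 121.

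**3. Power.** With about 10% lost, 121 − 12 = 109 per arm remain.

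| Per arm | Pooled | Continuity-corrected | Fisher |
|---|---|---|---|
| 109 | 83.5% | 78.6% | 80.0% |
| 121 (all outcomes retrieved) | 87.1% | 83.2% | 84.1% |

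The drop-out allowance covers most of the loss, so power is not the main issue.

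**4. What the missing outcomes could hide.** The documents give no withdrawal rate, only the 10% drop-out allowance. Assume m missing of 121 per arm, and 25% versus 10% detected among the n = 121 − m followed. Over all randomised:

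- lowest difference = [0.25n − (0.10n + m)] / 121
- highest difference = [(0.25n + m) − 0.10n] / 121
- missing counted as not detected = (0.25n − 0.10n) / 121

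For m = 12, n = 109: (27.25 − 22.90)/121 = 3.6 points; (39.25 − 10.90)/121 = 23.4 points; 16.35/121 = 13.5 points.

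For m = 6, n = 115: (28.75 − 17.50)/121 = 9.3 points; (34.75 − 11.50)/121 = 19.2 points; 17.25/121 = 14.3 points.

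The complete-case figure is 15.0 points in both cases. The outer limits are extremes, not forecasts.

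**5. Direction.** Let p be the true arm rate, w the share withdrawn and r the detection rate among those withdrawn. The observed rate is (p − wr)/(1 − w). Take true rates of 25% and 10%, with w = 0.10 in both arms.

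- Study-arm leavers 0%, control leavers 20% (twice their arm's rate): 0.25/0.90 = 27.8% and (0.10 − 0.02)/0.90 = 8.9%. The difference is 18.9 points.
- The mirror image, study-arm leavers 50% (twice their arm's rate), control leavers 0%: (0.25 − 0.05)/0.90 = 22.2% and 0.10/0.90 = 11.1%. The difference is 11.1 points.
- Leavers at their own arm's rate: 25% and 10%. The difference is 15 points, with no bias.

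**6. False-positive risk in the unfavourable direction.** Suppose there is no true effect (10% in both arms), 10% withdraw from each arm, study-arm leavers have 0% detection and control leavers 20% to 30%. The study arm shows 0.10/0.90 = 11.1%. The control arm shows (0.10 − 0.02)/0.90 = 8.9% down to (0.10 − 0.03)/0.90 = 7.8%. The spurious difference is 2.2 to 3.3 points. By normal approximation at 109 per arm, the two-sided 5% test rejects in 8.5% to 13.4% of trials.

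**The case against.** The strongest reply is that section 5.5.3 applies only to someone who wants to leave the study. Non-use of the recorder is treated elsewhere as a compliance matter (protocol 6.2, SAP 4.2.3), so such a participant stays enrolled and is followed through records. SAP 5.1.2 does not require a completed call, so a participant who declines calls can still have 90-day follow-up. Both points stand. A reader might infer that anyone who stops using the device is lost to the primary analysis; the text does not say so. What remains is that the text draws no line, and that people who do withdraw are never asked about the record check.

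A second reply is that missing data after full withdrawal do not in themselves contradict intention to treat. That also stands. A reader might take section 5.5.3 as the breach of protocol 8.2, but the direct contradiction is the treatment-received rule in SAP 5.1.

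A third reply concerns size. A reader might take the 18.9-point scenario as the expected bias in favour of the device. The documents do not support that. It treats the whole drop-out allowance as withdrawals and assumes leavers' detection rates that no passage gives. The mirror image is also plausible: a device user may leave once a rhythm has been captured, or a control without symptoms may lose interest.

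Finally, the information sheet and consent form may offer options on record access. The consent pages were not available for this review, so their wording cannot be judged. Even so, the protocol's own rule should say what sites must ask.

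**Conclusion.** The point holds as an avoidable gap in outcome collection and should be corrected. As written, protocol 5.5.3 gives up the planned record check for every participant who withdraws, and SAP 5.1.2 then excludes them. The loss is avoidable only for those who would allow the check; a refusal must be respected.

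Neither the size nor the direction of any bias can be stated from the documents. There is none if withdrawal is unrelated to outcome. The range of 3.6 to 23.4 points assumes that 12 of 121 are missing per arm and that the design rates hold among those followed; with 6 missing it narrows to 9.3 to 19.2 points. The documents establish neither a demonstrated bias towards the device nor a rule that stopping the recorder counts as withdrawal.

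**What to change.** 1. In protocol 5.5.3, state that stopping the recorder, the diary or contact is not withdrawal from the study.
2. At any withdrawal, ask whether the day-90 hospital and GP record check may continue. End data collection only if this is refused. Record the answer and any reason given, by arm.
3. In SAP 5.1.2, state that records-only follow-up counts as 90-day follow-up, and add a sensitivity analysis for primary outcomes that are still missing.
4. Analyse these participants in their allocated arm. This requires SAP 5.1 (treatment received) to be reconciled with protocol 8.2 (intention to treat); without that, the other changes do not deliver an analysis as randomised.

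The cost is wording in the protocol and SAP, and in the consent documents if they do not already cover it. The record review is already planned for both arms. Information available only by telephone will still be missing for these participants, and some will refuse record access, so the gap shrinks but does not close.
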